3.1 Summary of Prior Clinical Experience

LiteCure conducted two studies on the safety and efficacy of NIR-TLT applied to the forehead (prefrontal cortex) twice a week in subjects with MDD. The device used for ELATED-2 is a predicate device for EXPi-laser.

ELATED-1 was a 3-week proof-of-concept study of TLT (EXPi - class IV laser, wavelength 808 nm; irradiance 700 mW / cm²; fluence 84 J / cm²; total energy 2.4 kJ per session for 6 sessions) All subjects (n = 4) were treated with TLT. Mean baseline HAMD-17 scores for depression decreased from 19.8 ± 4.4 (SD) to 13 ± 5.35 (SD) after treatment ($p = 0.004$) (Cassano et al. 2015). (Cassano et al. 2015).

Near Infrared Transcranial Laser Therapy in Subjects with Major Depressive Disorder: A study of Dosing with Laser.

ELATED-2 was an 8-week double-blind, randomized, controlled study of TLT (Omnilux New U - LED, 823 nm; 36.2 mW / cm²; up to 65.2 J / cm²; vs. sham for 16 sessions). At completion, the mean HAMD-17 for depression decreased 11.7 ± 7.5 points (TLT, n = 9) vs. 5.3 ± 7.0 points (simulation, n = 9) (p = 0.04); the differences were even more pronounced in the completer sample as HAMD-17 decreased 15.7 ± 4.4 (TLT, n = 6) points vs. 6.1 ± 7.9 points (simulation, n = 7) (p = 0.01). (Cassano et al., 2018).

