4.4 Study Design

This study is a multicenter, randomized, sham-controlled, double-blind study on the use of transcranial continuous light therapy as a treatment for depressive symptoms in patients with major depressive disorder (MDD). Laser light therapy is tested in a strict parallel design.

This study will include 112 subjects randomly assigned to each of the four NIR-TLT treatment groups (28 subjects/group).

All subjects will receive three NIR-TLT treatments per week for 6 weeks and will complete a follow-up evaluation two weeks after treatment completion. All subjects and investigators (except the study statistician) will be blinded to treatment sequence assignment.

Energy will be administered at a wavelength of 808 nm, bilaterally to two frontal areas on the left and right side of the forehead, at or near electroencephalography sites F3 and F4. To maintain blinding, the treatment duration will be 429 seconds (7.15 minutes) for all groups. The treatment exposure (time during which the laser is active for the duration of the treatment) will be specific for each group, controlled by the device to normalize the treatment fluence of each active session per treatment location. Treatment will follow these specifications: wavelength 830 nm; average irradiance 350 mW / cm²; average fluence of 65.8 J / cm² (according to the parameters used in the ELATED-2 study at MGH with the Omnilux New U device) being the total fluence delivered: 3.6 kJ (bilateral) or 1.8 kJ (unilateral), either on the subject's forehead, at or near electroencephalography (EEG) sites F3 and F4.

The entire session (which includes the 429-second treatment and all procedures described in the "Study Visits" section) is estimated to take 30 minutes or less (Schiffer et al., 2009) (Lampl et al., 2007, Zivin et al., 2009). Additional time is needed to prepare the subject, fit the necessary protections (e.g., goggles), inspect the subject's skin, set up the NIR-TLT devices, and give the subject time to rest after irradiation. NIR-TLT treatment will only be administered by trained personnel who are on study staff. All personnel administering the treatment must pass laser safety training created by the American Institute for Medical Laser Applications and approved by the relevant Committees. The duration of irradiation will be decreased if clinically indicated, based on tolerability as needed.

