4.4.1 Randomization procedure

At screening, participants will be assigned an identification number on a first-come, first-served basis. When it is confirmed that the participant is eligible for the clinical trial, he/she will be randomized.

The assignment of each participant to a particular treatment arm (experimental and control group will be performed in a 1:1:1:1 ratio) will be done by using an electronic system, which is centrally administered.

Near Infrared Transcranial Laser Therapy in Subjects with Major Depressive Disorder: A study of Dosing with Laser.

For each participant at each visit, the investigator or center coordinator will communicate with the central statistician and, through a user and password assigned for the center, will enter the web system where he/she will be able to request and obtain the corresponding treatment number assigned to him/her in the study, and then proceed with the laser application. The participants and the study investigator will be blinded to the treatment assignment. The screen of the medical device does not show information of the dose applied to each participant, only the group to which he/she belongs will be referenced, keeping the dosing details confidential.

At central level, the unblinded statistician (responsible for administering this web system) will know which treatment arm corresponds to each participant from each research center.

4.4.2 *Blinding procedure*

This study is a clinical trial where blinding of both the investigator and the study participant will be assured. Only the treatment identifiers, the central statistician of the study, will know the treatment identifiers.

The sponsor is responsible for providing the medical device under study, programming and maintenance of the device.

The investigator at each center will be responsible for providing the corresponding dose according to the intervention under study (treatment assigned by the statistician through the web system) to each study participant.

Simulation blinding will be effective because the radiation is not visible and because no dose from the NIR-TLT will produce any perceptible difference from the simulation patient, e.g., skin heating.

4.4.3 *Contingency plan for opening of the blind*

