5.4 Baseline and Demographic Characteristics of the Subjects

The demographic and baseline characteristics of the subjects will be summarized for each treatment. Descriptive summaries will include number of subjects, mean, standard deviation, median, minimum and maximum for continuous parameters, frequencies and percentages for categorical parameters.

A t-test or chi-squared test, as appropriate for quantitative or categorical data, will be used to determine whether there were differences in the baseline demographic profiles of the groups. Differences were considered significant at p values <0.05 .

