5.5 Efficacy and Safety Analysis for the Aims

It will be carried out as follows:

A. Antidepressant effect of NIR-TLT doses:

To compare the antidepressant effects of NIR-TLT doses, mean changes in HAM-D 17 scores (for evaluation of the Primary Assessment Criteria) and QIDS-C and CGI-S (for evaluation of the Secondary Assessment Criteria), will be performed for each dose at 3 time points (visit 1, visit 9 and visit 18) will be compared using a repeated measures ANCOVA. A significant ANCOVA interaction in mean score changes between groups will be taken as indicating that the groups have different antidepressant efficacy. If significant ANCOVA interactions are found, paired samples t-tests will be used to explore differences between scores/groups.

Both the full analysis and the analysis by intention will be performed to analyze the severity of depression at the endpoint. Patient attrition and dropout will be analyzed. The possible

Transcranial Near Infrared Laser Therapy in Subjects with Major Depressive Disorder: A Laser Dosing Study.

differences between treatment groups in dropouts will be examined with Fisher's exact test.

B. Brain electrophysiological effect of NIR-TLT doses:

To compare the effects of NIR-TLT doses on brain electrophysiology, changes in EEG spectral power in all spectral bands for each dose at 3 time points (visit 1, visit 9, and visit 18) will be compared using a repeated measures ANCOVA. A significant ANCOVA interaction in mean score changes between groups will be taken as indicating that the groups have different effects. If significant ANCOVA interactions are found, paired samples t-tests will be used to explore differences between groups.

C. Safety and tolerability of NIR-TLT doses:

To compare the safety and tolerability of NIR-TLT doses, mean changes iSAFTEE-SI scores at 3 time points (visit 1, visit 9, and visit 18) will be compared using a repeated measures ANOVA. A significant ANOVA interaction in mean score changes between groups will be taken as indicating that the NIR-TLT doses have different tolerability. If significant ANOVA interactions are found, paired samples t-tests will be used to explore differences between groups.

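### Section 5.5 names paired-samples t-tests to compare four independent parallel arms, so the step that should identify the better dose has no suitable stated test

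*Protocol*

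**What the plan says.** The design has independent arms. Protocol section 4.4 states: "Laser light therapy is tested in a strict parallel design". Section 4.4.1 adds that allocation to "experimental and control group will be performed in a 1:1:1:1 ratio", and section 4.4 gives 28 participants per group. No matching of participants across arms is described.

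Section 5.5 analyses each outcome at visits 1, 9 and 18 with a repeated-measures ANCOVA (A and B) or ANOVA (C). A significant interaction is read as showing that the groups differ. The follow-up step is then:

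- **A (HAM-D17, QIDS-C, CGI-S):** "If significant ANCOVA interactions are found, paired samples t-tests will be used to explore differences between scores/groups".
- **B (EEG spectral power):** "If significant ANCOVA interactions are found, paired samples t-tests will be used to explore differences between groups".
- **C (SAFTEE-SI):** "If significant ANOVA interactions are found, paired samples t-tests will be used to explore differences between groups".

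No other test in the protocol compares one arm with another on these scores. Fisher's exact test is for dropouts and adverse events. The t-test in section 5.4 is for baseline profiles: "A t-test or chi-squared test, as appropriate for quantitative or categorical data, will be used to determine whether there were differences". On the analysis set, section 5.5 A says: "Both the full analysis and the analysis by intention will be performed to analyze the severity of depression at the endpoint".

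**The concern.** The interaction is a valid overall comparison of the arms, but it cannot say which arm is better. Hypothesis 1 (sections 4.1 and 5.2) predicts that the pulsed-wave dose is more effective, so it needs specific comparisons between arms. The only tool section 5.5 offers for that step is a test that requires paired observations, and independent arms supply none.

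The wording can be read in three ways, and none gives a usable between-arm test:

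1. **Paired within an arm, across visits.** This is a valid test of change from baseline, but it does not compare doses. Sham patients also improve, so sham would usually be significant, and so would an active dose no better than sham.
2. **Paired across arms.** There is no natural pairing. At equal arm sizes the test keeps its level and estimates the between-arm difference, but its p-value depends on the arbitrary order of the rows. At unequal sizes participants must be discarded to form pairs.
3. **Pairwise was intended.** The text then names the wrong test.

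At stake is the dose conclusion: which dose beats sham, and whether pulsed beats continuous light.

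**Working it through.** **Inputs.** From section 5.3: active change −10.8, SD 7.55; control change 4.4, SD 6.65; difference 6.4; common SD 7.091; alpha 0.05; power 90%; 20% loss; 28 per arm. The control change is read as a fall of 4.4, because 10.8 − 4.4 = 6.4. From section 3.1 (ELATED-2): sham falls of 5.3, SD 7.0 ("vs. 5.3 ± 7.0 points (simulation, n = 9) (p = 0.04") and 6.1, SD 7.9 (completers). Assumptions: changes are normal; evaluable n = 28 × 0.8 = 22.4, rounded down to 22; tests are two-sided at 0.05 unless stated.

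**The plan's own figure.** For two independent samples with difference 6.4 and SD 7.091, a one-sided 0.05 test needs 22 per arm (power 0.903). Then 22/0.8 = 27.5, rounded up to 28, and 4 × 28 = 112, as stated. A two-sided test would need 27 per arm, or 34 after loss and 136 in total. So 112 is reproduced as an unpaired comparison of two arms (one-sided), and the follow-up test in 5.5 does not match that basis.

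**Reading 1, paired within an arm.** The noncentrality is mean change / (SD/√n), with n − 1 degrees of freedom.

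| Arm | n = 22 | n = 28 |
|---|---|---|
| Sham, 4.4 / 6.65 | 3.10, power 0.84 | 3.50, power 0.92 |
| Sham, 5.3 / 7.0 | 3.55, power 0.92 | 4.01, power 0.97 |
| Sham completers, 6.1 / 7.9 | 3.62, power 0.93 | 4.09, power 0.98 |
| Active, 10.8 / 7.55 | 6.71, power >0.999 | 7.57, power >0.999 |

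A working dose and a dose that only equals sham would both be significant with probability 0.841 × 1.000 = 0.84 at 22 per arm.

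**Reading 2, paired across arms at equal n.**

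- *Power.* The SD of an arbitrary pair difference is √(7.55² + 6.65²) = 10.06. At n = 22 the noncentrality is 6.4/(10.06/√22) = 2.98. Power is 0.812 on 21 degrees of freedom paired, and 0.830 on 42 unpaired. At n = 28 it is 0.900 against 0.911.
- *Level.* Under the null at n = 22, simulation (200,000 runs, SD 7.091) gives 0.049 paired and 0.050 unpaired.
- *Row order.* A trial is counted as order-dependent if between 5% and 95% of random orderings are significant. In 20,000 simulated trials with 200 orderings each, this held in 19.0% of trials at n = 22 and 10.7% at n = 28. With the all-subjects ELATED-2 figures in section 3.1 (11.7, SD 7.5 against 5.3, SD 7.0) it was 20.0% and 11.7%.
- *Illustration.* In one simulated data set with 22 per arm, the unpaired p was 0.0003. Across 5,000 random pairings of the same data, the paired p ran from 0.000003 to 0.005.

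**Reading 2 at unequal n (complete cases).** With evaluable numbers distributed Bin(28, 0.8), the probability that two arms differ in size is 1 − Σp² = 0.867. At 5% loss it is 0.744. The mean absolute difference in size at 20% loss is 2.37. Given unequal arms it is 2.37/0.867 = 2.73 participants, who would be discarded to force pairs.

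**The case against.** **The step is exploratory and gated.** The interaction is the decision rule, and the t-tests run only if it is significant. This stands: the overall conclusion that the groups differ does not rest on the follow-up sentence. But that sentence is the only route from a difference among the groups to a statement about which dose is better.

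**The row-order rates ignore the gate.** This stands as a qualification. With a one-way F-test on change in four arms as a simplified gate, order dependence falls to about 14–18% at 22 per arm and 8–10% at 28. The within-arm sham figure barely moves (0.81–0.84 at 22).

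**Nobody would pair unrelated patients by file order.** It is the least plausible reading, and its power cost is only about two percentage points. The discarded-pairs figure also needs a complete-case analysis. If all 28 per arm are kept in the analysis by intention, sizes can be equal and only the row-order problem remains. The within-arm result is therefore the stronger argument.

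**Part A refers to scores as well as groups.** A paired test between visits is legitimate for scores. That does not supply a test between groups, and B and C refer to groups only.

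**Pairwise may simply have been mistranslated.** This is possible. Section 5.4 uses an unqualified t-test for differences between groups, which makes the wording in 5.5 look like a specific choice, though the English is loose enough that this proves little. Either way the sentence must change.

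**A statistical analysis plan may settle it.** The protocol does not leave the test open. It names an unsuitable one three times, so an analysis plan would have to contradict the protocol or inherit the error.

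**Conclusion.** The concern holds. Section 5.5 A, B and C name a test that does not fit four independent arms, and no reading turns it into a suitable between-arm comparison. The damage is confined to naming the better arm. The interaction test stands, and the sample size is unaffected because it was computed from a between-group difference.

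For HAM-D17, read within an arm, sham alone would be significant with probability 0.84–0.93 at 22 per arm and 0.92–0.98 at 28, depending on which of the protocol's sham figures is used. Such tests cannot separate an effective dose from an ineffective one. Read across arms, two analysts with the same data could reach different verdicts in about 19% of trials at 22 per arm and 11% at 28, somewhat less once the interaction is required to be significant. These figures rest on normal changes, two-sided 0.05 and a fall of 4.4 in the section 5.3 control group. The protocol gives no figures from which to size the effect for EEG or SAFTEE-SI. This should be fixed.

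**What to change.** In section 5.5 A, B and C, replace the paired-samples t-tests with between-arm contrasts from the fitted repeated-measures model, or with independent-samples tests of change. These should cover each active arm against sham and the pulsed-against-continuous comparisons that Hypothesis 1 needs. Whether the two pulsed arms are taken separately or together is the sponsor's choice and should be stated. Within-arm change can still be reported, as description only. If pairwise comparisons were meant, say so and name the independent-samples test.

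The cost is one sentence in each of the three parts, with no new data, visits or participants. The change should be made before unblinding, so that the choice of test cannot be influenced by the results.

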4.7 Sample Size

The study is expected to include 112 subjects with analyzable data (at least 3 sessions - 1 week, after randomization).

Near Infrared Transcranial Laser Therapy in Subjects with Major Depressive Disorder: A study of Dosing with Laser.

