4.19 Subject Disposition Criteria

4.19.1 Withdrawal from the Study

Each subject and the investigator reserve the right at any time to terminate a subject's participation in the clinical investigation.

Possible reasons for withdrawal or removal from the study may include:

Transcranial Near Infrared Laser Therapy in Subjects with Major Depressive Disorder: A Laser Dosing Study.

1. The subject voluntarily withdraws consent.
2. The subject was ineligible according to the inclusion and exclusion criteria of the study.
3. The subject develops an adverse event that would not allow continuation in the study.
4. The subject has an adverse event that, in the opinion of the investigator, warrants withdrawal from the study. Pthera LLC must be notified within two business days.
5. The subject and/or the investigator make the decision that the subject should withdraw from the study.
6. Subject to death of participant.
7. Positive pregnancy test during eligibility procedures.
8. The subject misses one of the 3 scheduled sessions per week and it is not possible to make it up before the end of the week. When a subject withdraws or is withdrawn from the study, the following will be performed, if possible, at the study termination (exit) visit:
 - HAM-D-17
 - QIDS-C
 - CGI
 - C-SSRS
 - ADVERSE EVENT FORM
 - Concomitant Medication Form
 - ASQ (self-assessment)
 - SAFTEE-SI (self-assessment)
 - SDQ (self-assessment)

For all subjects who prematurely withdraw from the study, the date and reason for withdrawal will be documented.

4.19.2 *Loss of Follow-up*

If a center is unable to contact a subject or if the subject fails to appear for a visit, three documented telephone calls should be made, followed by a certified letter (or its equivalent, such as an e-mail). The certified letter should detail the need for the subject to appear for a visit, the center's failed attempts to contact the subject, and that failure to contact the center will cause the subject to be withdrawn from the study.

If the certified letter is returned to the center as undeliverable or the letter is delivered but the subject does not communicate with the center and no further contact is made with the subject or the subject's caregiver, then the subject will be considered lost to follow-up with the subject and suspended from the study. All attempts to contact the subject will be documented.

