5.3 Sample Size

The sample size was determined using G Power software version 3.1, considering a calculation by double mean difference with common standard deviation, assuming a significance level of 0.05 and 90% power. The parameters used were obtained from page 7 (section "Antidepressant effect according to clinician-rated measurement") of the previous ELATED-2 study (Cassano et al., 2018), where the mean difference of the HAM-D17 score for the experimental group was -10.8 ± 7.55 and for the control group 4.4 ± 6.65 ; such data identify a double difference of 6.4 with common standard deviation of 7.091. With this information, a total sample of 112 participants is obtained, taking into consideration a 20% loss rate. Each group will have 28 participants.

With $n=112$, in 4 groups in a longitudinal design, we estimated a power of 90% to differentiate ($\alpha=0.05$) the therapeutic effect of the dose, giving an antidepressant effect and an effect variance equivalent to that obtained in participants who completed the ELATED-2 study for all groups (Cassano et al., 2018b)

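### Section 5.5 A gives the primary HAM-D-17 outcome two analyses without saying which decides, and its repeated measures ANCOVA in classical form does not deliver the intention-to-treat one

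*Protocol*

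**What the plan says.** Section 5.5 A compares mean HAM-D-17 changes across the four groups at visits 1, 9 and 18 by repeated measures ANCOVA. It then adds: "Both the full analysis and the analysis by intention will be performed to analyze the severity of depression at the endpoint". Neither analysis is called primary, and no rule covers disagreement. The section also says that attrition will be analysed and dropout compared between groups by Fisher's exact test. It gives no rule for missing values.

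The number 112 appears in three roles:
- Section 4.7 expects "112 subjects with analyzable data (at least 3 sessions - 1 week, after randomization").
- Section 4.5.1 describes 112 randomised subjects.
- Section 5.3 states that "a total sample of 112 participants is obtained, taking into consideration a 20% loss rate".

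On the pilot trial ELATED-2, section 3.1 gives HAM-D-17 decreases of 11.7 versus 5.3 points (9 per arm) and then reports that "the differences were even more pronounced in the completer sample as HAMD-17 decreased 15.7 ± 4.4 (TLT, n = 6) points", against 6.1 in 7 sham completers.

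**The concern.** Two unranked analyses of one primary outcome leave open which result counts. If they disagree, the protocol does not say whether an antidepressant effect has been shown.

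The stated method adds to this. A classical repeated measures ANCOVA needs a value at every visit in the model, so a participant without visit 18 drops out of it. An analysis by intention cannot be obtained that way unless something is added for those people, and section 5.5 A adds nothing.

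Loss is planned at 20%. It can follow tolerability, worsening or missed sessions, any of which may differ between laser and sham. An analysis restricted to people with complete data can then be biased, in either direction.

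**Working it through.** **1. The plan's own figure.** Inputs from section 5.3: "assuming a significance level of 0.05 and 90% power"; "such data identify a double difference of 6.4 with common standard deviation of 7.091"; 20% loss; "Each group will have 28 participants".

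n per arm = 2 × (z for alpha + z for power)² × (SD / difference)² = 2 × (1.645 + 1.282)² × (7.091 / 6.4)² = 2 × 8.567 × 1.228 = 21.0, taken up to 22 (a t-based calculation gives 21.7, also 22). Then 22 / 0.80 = 27.5, so 28 per arm, and 28 × 4 = 112.

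The figure reproduces with a one-sided alpha of 0.05. Section 5.3 does not state sidedness; that is a separate matter. What matters here is that the calculation treats lost participants as contributing nothing, which fits a complete-case analysis better than an intention-to-treat one.

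**2. The three uses of 112.**
- If 112 are randomised (4.5.1) and 20% are lost (5.3), 112 × 0.80 = 89.6 have complete data, or 22.4 per arm.
- If 112 are to be analysable after that loss, 112 / 0.80 = 140 must be randomised, or 35 per arm.
- Section 4.7 agrees with the other two only if every randomised person has at least three sessions and all loss comes later.

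**3. Precision by set.** One pairwise t-test, difference 6.4, SD 7.091, two-sided 0.05:

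| Set | n per arm | Power |
|---|---|---|
| All randomised, outcomes for all | 28 | 91.3% |
| Complete cases, 20% loss | 22.4 | 83.9% |
| Complete cases, pilot's loss of 5/18 = 27.8% | 20.2 | 79.9% |

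**4. The pilot, from the summary figures in section 3.1.**

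| | 9 vs 9 | Completers, 6 vs 7 |
|---|---|---|
| Difference | 11.7 − 5.3 = 6.4 | 15.7 − 6.1 = 9.6 |
| Pooled SD | √[(7.5² + 7.0²)/2] = 7.25 | √[(5 × 4.4² + 6 × 7.9²)/11] = 6.55 |
| Standardised difference | 0.88 | 1.47 |
| Standard error | 7.25 × √(2/9) = 3.4 | 6.55 × √(1/6 + 1/7) = 3.6 |
| Two-sided p | 0.080 | 0.023 |

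The completer difference is 9.6 / 6.4 = 1.5 times the other. At two-sided 0.05 the conclusion changes with the set. The p values quoted in section 3.1 (0.04 and 0.01) match one-sided tests, under which both sets are significant. Section 5.3 attributes its assumptions to pilot participants who completed, yet its 6.4 equals the 9 versus 9 difference.

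**5. How often two sets would disagree.** Simulation with 28 per arm, SD 7.091 and one two-sided pairwise t-test, comparing all randomised (outcomes assumed known for everyone) with completers. The dropout patterns are assumptions.
- True difference 6.4, random loss: the sets disagree on significance in about 10% of trials at 20% loss and 14% at 27.8%.
- Difference 6.4 in completers, none in dropouts: disagreement is about 15% and 22%. Power is 72% (all randomised) versus 83% (completers) at 20% loss, and 63% versus 79% at 27.8%.
- No true difference, either set accepted: error rises from 5% to about 7% to 8% with random loss. If active-arm dropouts do worse by 3 or 6.4 points at 20% loss, it is about 8% or 12%; the completer bias is then 0.20 × 3 = 0.6 or 0.20 × 6.4 = 1.28 points.

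**6. Bias of complete cases.** Assume 20% loss after visit 9, linked to visit 9 response differently by arm, a visit 9 to visit 18 correlation of 0.6 and a true difference of 6.4. Complete cases then give about 5.6 to 7.3 points with a moderate link and about 4.5 to 8.3 with a stronger one. An analysis using visit 9 data from everyone returns 6.4, as it must when dropout depends only on observed values. The documents give no basis for the correlation or the strength of the link.

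**The case against.** The strongest reply is that section 5.5 A promises an analysis by intention, so dropouts are meant to be kept, and that set definitions and missing-data handling commonly sit in a statistical analysis plan, which is not at hand. This stands as far as it goes: absent definitions are not the point, and complete-case handling is inferred from the named method. It does not answer the lack of ranking, because the protocol itself commits one primary outcome to two analyses.

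The full analysis may also mean a full analysis set. The two sets could then nearly coincide, and the completer figures above would overstate the effect of the choice.

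Several stronger readings are tempting, but the documents do not support them:
- A reader might infer that section 4.7 defines an analysis set by sessions received. It is a recruitment expectation, and section 5.5 A does not refer to it.
- A reader might infer from section 4.19.1 that randomised people later found ineligible are left out of the analysis. "The subject was ineligible according to the inclusion and exclusion criteria of the study" is listed only as a possible reason for withdrawal from the study, and the list also covers events before randomisation.
- A reader might infer that someone with 3 to 7 sessions has no post-baseline HAM-D-17. The Table of Assessments shows none from V2 to V8, but section 4.9.2 lists the scale at treatment visits, and section 4.19.1 asks for it at an exit visit where possible. The text contradicts itself; it does not establish that no value exists.
- A reader might infer that the sponsor is free to report the favourable set. Section 5.5 A says both analyses will be performed, and section 4.16 commits to publishing negative as well as positive results.

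Retention also helps: section 4.9.4 encourages participants to stay through follow-up after stopping treatment. Sections 4.19.1 and 4.19.2, however, provide for withdrawal when a week's sessions are not completed, so it is unclear how far that encouragement applies.

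**Conclusion.** The point holds in a limited form. Section 5.5 A names two analyses of the primary outcome without a primary one, and the method it specifies would not, in classical form, give an intention-to-treat result with 20% loss. That second part assumes the classical form, since no missing-data rule is stated.

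The pilot shows that the set can matter, but not by how much. A gap of 9.6 − 6.4 = 3.2 points, with standard errors of 3.4 and 3.6 on overlapping samples, is no estimate of bias. Under moderate assumed dropout the complete-case bias is below 1 point in either direction; under stronger dropout it is larger. Under the assumptions tried, two sets disagree on significance in about 10% to 22% of trials when the completer effect is 6.4, and accepting either raises the two-sided error from 5% to about 7% to 12%.

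This is a worthwhile, inexpensive correction, below the level of something that must be fixed before the trial can proceed.

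**What to change.** - **5.5 A.** Name one primary analysis: all randomised participants in the arm assigned, fitted with a likelihood-based mixed model for repeated measures that uses every available post-baseline HAM-D-17 value. Enter exit-visit values at their actual time or in a prespecified post-baseline window, never at V1, so that an early exit value is not treated as baseline. Make the completer analysis a sensitivity analysis.
- **4.7.** Remove the three-session wording as a condition for being analysed. Reconcile 112 analysable with 112 randomised (4.5.1) and 112 including 20% loss (5.3).
- **Collection of the outcome.** Reconcile section 4.9.2 with the Table of Assessments on the visits at which HAM-D-17 is collected.
- **Withdrawal and retention.** Reconcile sections 4.19.1 and 4.19.2 with section 4.9.4. No clinical rule is proposed here; the passages only need to agree, so that it is clear which outcome data are sought after treatment stops.

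The change to the analysis is wording in the protocol and any analysis plan, needs no new data, and should be made before unblinding. The downside is that the all-randomised estimate may be smaller than the completer estimate. The mixed model also relies on dropout being explained by observed values, which the sensitivity analyses should acknowledge.
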